**Adjunctive Nitrous Oxide during ED propofol sedation in adults,
a pilot study.**

NCT02410707

Version: 7/1/14

Investigator(s): [name], DO; [name], DO; [name]; [name], CCRC

Objectives

To describe the safety and efficacy of adjunctive nitrous oxide pre-propofol administration for analgesia and pre-procedure anxiolysis during ED procedural sedation and analgesia in adults.

Background

Specific Aims

To measure the rates of hypoxia and respiratory depression requiring a physician intervention in adult patients receiving 50% demand valve nitrous oxide pre-propofol administration during ED procedural sedation and analgesia. Secondary aims include patient, nursing, and physician post procedure satisfaction scores, Ramsay sedation scores, total propofol dose given, length of time spent using nitrous oxide, patient recall of procedure.

Significance

Procedural sedation is the use of sedative, analgesic, and/or dissociative agents to relieve anxiety and pain associated with diagnostic and therapeutic procedures. Propofol has become one of the most commonly used agents for ED procedural sedation.^{1,2} Propofol crosses the blood-brain barrier rapidly. The drug takes effect within approximately 40 seconds, and its

duration of action is approximately six minutes^{2,3} Multiple randomized trials and prospective observational studies have found propofol to be safe and effective for PSA in the emergency department^{3,4,5}. Propofol acts as a sedative and amnestic, but provides no analgesia.

A possible approach is pretreatment with short-acting opioids (eg, fentanyl). Unfortunately, the addition of opioids increases the likelihood of respiratory complications. As an example, fentanyl at a dose of 1.5 mcg/kg increases the risk of respiratory depression. In another study, patients given both alfentanil and propofol required stimulation to induce respiration more often than those given only propofol.⁷ Another alternative to pretreatment with short-acting opioids is to use sub-dissociative doses of ketamine (0.3 mg/kg). Ketamine appears to provide comparable analgesia with less risk of respiratory depression. However, there is no literature that has shown that there is a decreased risk of respiratory depression than with propofol.⁸

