The optimal agent for analgesia before procedural sedation would have effect that is short acting, easy to administer, and with minimal risk to the patient. Nitrous oxide may fit this profile. In pediatric emergency departments, inhaled nitrous oxide was found to be the most common agent for procedural sedation and analgesia.⁸ There is a great deal of literature supporting the use of nitrous oxide in the pediatric population, and the safety and efficacy of its use as a single agent or in concert with a parenteral sedative and/or analgesic is excellent. However, there is a paucity of literature to support or refute the use of nitrous oxide in adults for ED procedural sedation and analgesia.

Nitrous oxide is a colorless gas that diffuses rapidly across the pulmonary alveoli providing analgesia and anxiolysis with minimal sedative effects, rapid induction, and emergence.⁹ Nitrous oxide is a weak sedative agent with the potential for significant analgesic

effects. Noncompetitive antagonist activity at the NMDA receptor along with activation of opioidergic receptors contributes to its anesthetic mechanism.¹⁰ In an RCT (ENIGMA 1) using anesthesia with and without nitrous oxide, there was a small increased risk of myocardial infarction in the nitrous oxide group.¹¹ However, there were patients getting general anesthesia for over two hours; our patients will be receiving 50/50 nitrous oxide for 5-10 minutes maximum, and there are no known cardiac side effects reported during short-term sedation in the literature.¹¹ There are rare adverse events, most often cited as case reports of chronic or acute toxicity causing myeloneuropathies and polyneuropathies.¹²⁻¹⁵

Nitrous oxide has been used in general anesthesia for over 2 centuries, but its use outside of the operating room began when Tunstall introduced the nitrous oxide/oxygen mixture as an analgesic agent during labor.¹⁶ Since this inception, the nitrous oxygen/oxygen mixture has been used readily in the fields of dentistry, gastrointestinal procedures, and children's procedural sedation. Nitrous oxide is often administered via continuous flow or on-demand at a concentration of 50-70%.

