We believe that pre procedure adjunctive nitrous oxide may provide a level of anxiolysis and analgesia before propofol is administered, leading to a smoother and more satisfactory sedation and procedure, with fewer adverse respiratory events and less overall propofol dose than propofol alone. Since this is a novel concept, we believe that a pilot study to evaluate the safety and efficacy of pre-procedure adjunctive 50/50 nitrous oxide administration with adult propofol administration is warranted.

Setting of the Research

Patients will be recruited from the Emergency Department of Einstein Medical Center Philadelphia. The Einstein Medical Center Philadelphia is an urban teaching hospital, level one trauma center with 500 beds and an annual ED census of 100,000 subjects.

Resources Available to Conduct this Research

The Einstein Medical Center Philadelphia ED sees approximately 300 patients a day, of which 5% are emergencies that require procedural sedation and analgesia, and thus will be available as potential subjects in this study. The Division of Clinical Research of the Department

of Emergency Medicine has extensive experience in both investigator led and pharmaceutical research. This will be the seventh trial we have conducted in our ED in procedural sedation and analgesia in the last 7 years, and each of these studies has recruited 100-200 patients. We have a research associate 7 days a week who will consent and enroll eligible patients. The division also has 2 full time coordinators and a full time division director, as well as biostatistician support. We have two well-equipped offices, one in the ED where the research associate is based and one in our department where our division director works. The lead investigator will lead 10% of their non-clinical time to this endeavor.

Study Design

This pilot study will be conducted in a prospective, non-randomized fashion using a convenience sample of 100 subjects undergoing sedation for ED procedures.

1. Recruitment Methods

The research associates as well as the health care team (both residents and attending physicians) will screen patients who may need procedural sedation in the ED and may qualify for the study. Research associates will use the Cerner/AeCIS System for screening, and they will be in charge of informed consent, enrollment, placement of the capnography monitor, as well as data collection. The health care team will be in charge of the procedural sedation and all other management.

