The SEDARA gas mixer system [Linde Gas North America LLC] will be used as our primary nitrous oxide delivery device. It will mix and deliver nitrous oxide and oxygen in a 1:1 ratio, at a fixed concentration of 50%/50%. It uses a patient driven demand valve system that is hand held. This device provides a consistent, fixed 50%/50% blend of nitrous oxide (N₂O) and oxygen (O₂), eliminates the need to titrate, and provides fixed concentrations for controlled and consistent dosing. The device comparator detects dosing imbalance to protect against hypoxic mixtures, it cannot deliver nitrous gas without concurrent oxygen, and the device has an anti-asphyxia valve override. The on demand valve requires patient inspiration to trigger dosing. This portable device scavenges exhaled waste gases for environmental safety, as well as a key mechanism that renders the system inoperable without it for security.

After informed consent, the patient will fill out a pre procedure questionnaire and a 100 mm VAS baseline pain scale. The patient will be given the mask for delivery of nitrous oxide, and instructed on its use. The research associate will mark the time the patient began using the device electronically on the capnostream 20. Once IV access is established, and the team and

patient are ready to begin the procedure, the nitrous oxide mask will be removed, and a 100% NRB mask delivering 15 liters a minute of supplemental oxygen will be placed on the patients face. The loading dose of propofol will then be administered immediately. All sedations in this trial will use propofol 1.0 mg/Kg initial dose, with 0.5 mg/Kg doses titrated to deep sedation. Once the patient is deeply sedated, the procedure will begin.

The subject's clinical data and sedation information (refer to data management) will be entered into a standardized data collection form. The data will be continuously recorded throughout the sedation and recovery periods. Study will end when the subjects recovers back to baseline mental status.

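### Respiratory safety is the primary aim of a combination the plan calls novel, yet no review of accumulating events is tied to enrolment, no event rate requires a pause, and withdrawn subjects' data are deleted

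*Combined protocol and SAP*

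**What the plan says.** The Objectives section sets out "To describe the safety and efficacy of adjunctive nitrous oxide pre-propofol administration", and Specific Aims puts rates of hypoxia and of respiratory depression needing intervention first. Significance says of the evidence that "there is a paucity of literature to support or refute the use of nitrous oxide in adults", and gives the rationale: "Since this is a novel concept, we believe that a pilot study to evaluate the safety and efficacy". On design: "This pilot study will be conducted in a prospective, non-randomized fashion using a convenience sample of 100 subjects undergoing sedation for ED procedures".

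Safeguards for each subject are set out in detail. Eligibility is limited to ASA class 1 or 2, with exclusion for cardiopulmonary instability or at the physician's discretion. Exposure is short: "our patients will be receiving 50/50 nitrous oxide for 5-10 minutes maximum". On the equipment, "The device comparator detects dosing imbalance to protect against hypoxic mixtures". Section 4 has the nitrous oxide mask taken off and 15 L/min oxygen started before propofol, and interventions are flagged electronically.

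Three provisions bear on counting events:

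- Section 5: three investigators code every graph. No timetable is given and no action follows from the result. A graph with more than 35% data loss is dropped unless all three see unequivocal hypoxia or respiratory depression.
- Section 6: when a subject chooses to withdraw, the data are deleted; only the number of withdrawals is kept.
- Statistical Plan: descriptive summaries and correlations only. Sample Size Determination expects hypoxia in roughly 10-30% with propofol and uses no power calculation.

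**The concern.** When 10-30% of sedations are expected to include hypoxia, a single desaturation looks ordinary. An excess shows only when events are totalled and set against a reference. The plan collects what is needed for that total but never requires anyone to form it while enrolment is open. The expectation that nitrous oxide will reduce respiratory events is a hypothesis, which the plan itself says adult evidence can neither support nor refute.

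The deletion rule works against the primary aim directly. A subject who desaturates and then withdraws leaves the numerator and the denominator, and only the fact of withdrawal remains.

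**Working it through.** **The plan's own figure.** The 100 rests on no alpha, power or precision target, so there is nothing to reproduce. As written, expected enrolment is 100 at any event rate.

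**An illustrative limit.** Inputs: reference 30% (top of the plan's range); looks at 25, 50 and 75 treated subjects (my choice); event SpO2 below 92% (the cut-off in section 4, assumed to match the plan's undefined hypoxia figure); subjects independent. The boundary k is the smallest count whose one-sided 95% exact (Clopper-Pearson) lower limit exceeds 0.30, that is, P(X ≥ k | n, 0.30) < 0.05:

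- n = 25: k = 12, tail 0.044
- n = 50: k = 21, tail 0.048
- n = 75: k = 30, tail 0.041

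Exact binomial recursion over the three looks gives:

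| True hypoxia rate | P(limit crossed) |
|---|---|
| 20% | 0.002 |
| 25% | 0.016 |
| 30% | 0.09 |
| 35% | 0.30 |
| 40% | 0.62 |
| 50% | 0.98 |

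**Enrolment, only if a pause is permanent.** With 10 more subjects entering during coding, stops fall at 35, 60 or 85:

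- True 40%: 35×0.268 + 60×0.218 + 85×0.137 + 100×0.378 ≈ 72.
- True 50%: 35×0.655 + 60×0.257 + 85×0.065 + 100×0.024 ≈ 46.

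**Deletion.** Suppose 30 of 100 are hypoxic and 5 withdraw. If all 5 were hypoxic (worst case), the reported rate is 25/95 = 26.3%; if none were, it is 30/95 = 31.6%. For the limit above at a true 40%, deleting hypoxic subjects equal to 2% or 5% of all subjects lowers the chance of crossing from 0.62 to 0.52 or 0.38.

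**Heavy-loss graphs.** The section 5 clause keeps a heavy-loss graph only when it shows an event. With 20% heavy loss unrelated to hypoxia (assumed), and every such hypoxic graph judged unequivocal, a true 30% appears as 0.30/(0.30 + 0.70×0.80) = 34.9%. Simulation, with the boundary recomputed at the evaluable number, gives P(limit crossed):

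| Heavy loss (assumed) | True rate | Hypoxic heavy-loss graphs counted | All heavy-loss graphs dropped |
|---|---|---|---|
| 10% | 30% | 0.14 | 0.07 |
| 20% | 30% | about 0.25 | 0.07 |
| 30% | 30% | 0.40 | 0.07 |
| 30% if hypoxic, 15% if not | 40% | 0.79 | 0.26 |

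Dropping them avoids false alarms, but it loses most of the detection if loss is commoner in hypoxic subjects. Adding a hypoxic subject to both numerator and denominator can only raise the lower limit. So if either count may trigger review, the count that includes these graphs decides, and the other helps interpretation.

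**Assisted ventilation.** The plan gives no rate, so no threshold can be derived. At assumed rates of 1%, 2% or 5%, 1 − (1 − q)^100 gives 0.63, 0.87 or 0.99 for at least one event, with 1, 2 or 5 expected.

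**Enrolment time.** Resources says the department "sees approximately 300 patients a day, of which 5% are emergencies that require procedural sedation and analgesia": 300×0.05 = 15 a day. At an assumed 10-25% uptake (1.5 to 3.75 a day), 100 subjects take 67 to 27 days. The same section calls this the seventh sedation trial in 7 years, each recruiting 100-200. Six earlier trials make 600-1,200 subjects in 7 years, about 86-171 a year, so 100 take about 7-14 months, ignoring gaps and overlaps.

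**The case against.** The strongest reply is proportionality. This is a single-site descriptive pilot in low-risk adults, with short exposure, continuous monitoring and flagged interventions. A short requirement for periodic review, plus review of each assisted ventilation, would close most of the gap. That largely stands: the review and the withdrawal change are the core, and the numerical limit is a judgement added to them.

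The limit is also blunt. If this site's background were 10%, a doubling to 20% would cross it with probability 0.002 and a tripling to 30% with 0.09. It must not be presented as protection against a rise within the plan's own range. A running count seen by the people who code the graphs could also colour later coding.

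Five stronger readings are tempting, and the documents do not support them:

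- That subjects are unprotected, or that nobody would act. The bedside safeguards are extensive, and ad hoc action by the investigators or IRB is not excluded.
- That enrolment will close within weeks, before coding can finish. That follows from an assumed uptake; the site's own record points to many months.
- That a limit would spare 28 or 54 subjects at true rates of 40% or 50%. A pause leads to review, and enrolment may resume.
- That heavy-loss graphs should simply leave the safety count. Under informative loss this hides harm (0.26 against 0.79).
- That deletion also covers subjects withdrawn for failed recording. Section 6 attaches it to subjects who choose to leave and is silent on the others.

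**Conclusion.** The gap is real and should be closed; confidence is medium. The plan links no cumulative review to enrolment, requires no pause at any rate, and has a deletion rule that can bias its primary rate. The omission and the deletion rule rest on the text alone. The operating characteristics rest on the chosen looks, the 30% reference, the assumed event definition and independence. The loss, withdrawal, uptake and ventilation figures are assumptions. The plan does not define the event behind its 10-30%; if ordinary care at SpO2 below 92% runs at 35%, the chance of an unnecessary review is about 0.30 rather than 0.09. The documents do not show that the combination is harmful or that subjects lack bedside protection.

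**What to change.** 1. **Section 6.** Replace the deletion sentence so that de-identified safety events before withdrawal are kept, and say so at consent.
2. **Study Design, review.** Add: 'The three investigators will code graphs in batches and, with the study biostatistician, review cumulative hypoxia and interventions after 25, 50 and 75 treated subjects. Each positive pressure ventilation or intubation is reviewed when it occurs. The decision on continuing enrolment is recorded each time.'
3. **Study Design, trigger.** Add: 'Enrolment pauses for investigator and IRB review if the one-sided 95% exact lower limit for peripheral hypoxia (SpO2 below 92%) exceeds 30% (12/25, 21/50 or 30/75, recomputed at the evaluable number). This guards against gross excess only. The count is shown with and without heavy-loss graphs bearing unequivocal hypoxia, and either crossing the limit prompts review.'

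Cost: a protocol paragraph, one withdrawal sentence matched at consent, and coding in four batches. No new committee or measurement is needed. The coders are already named, and the Resources section notes: "The division also has 2 full time coordinators and a full time division director, as well as biostatistician support". The price is some unnecessary reviews: about 9% of trials at a true 30%, about 30% if ordinary care runs at 35%, and 14-40% at a true 30% with 10-30% heavy loss. Coders would also see a running count.

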2. Inclusion and Exclusion Criteria

- i. Inclusion criteria: All spontaneously breathing subjects, 18 years of age and older, with an American Society of Anesthesiologists (ASA) Physical Status Classification 1 or 2, who will be receiving sedation for an ED procedure.

Written informed consent will be obtained from all subjects.

- ii. Exclusion criteria: Subjects with underlying conditions that could affect ventilation, perfusion, or metabolism including intubated subjects, subjects with clinical signs of cardiopulmonary instability, major trauma, shock, sepsis, ASA class 3, 4, and 5. Also those unable to provide informed consent, nursing home residents, age less than 18 years, non English speaking, pregnant women, subjects under police custody, or physician discretion.

3. Study Endpoints

- i. Primary:

1. ETCO₂ measured q 20 milliseconds seconds
2. SpO₂ measured q 20 milliseconds seconds

- ii. Secondary Endpoints

1. A baseline reading of the vital signs (heart rate, respiratory rate, peripheral SaO₂ and ETCO₂)
2. Physician interventions (verbal or physical stimulation, airway repositioning, additional oxygen, positive pressure ventilation, endotracheal intubation)
3. Level of sedation (Ramsay Score)
4. Patient Demographics
5. Patient recall of procedure
6. Total propofol dose
7. Total elapsed time of nitrous oxide use
8. Patient and physician procedure satisfaction score

4. Procedures Involved in the Research

Initial medical assessment will be made in accordance with established clinical procedures, including the history, physical examination, and vital signs. If by clinical assessment the patient meets eligibility criteria, then they will be approached by a research associate for enrollment in the study. After informed consent is obtained and prior to starting the sedation, standard vital sign monitoring will be placed on the patient (electrocardiogram, non-invasive blood pressure monitoring, pulse oximetry, and capnography). Level of consciousness will be determined using the modified Ramsay scale, which will be assessed at baseline. The Capnostream 20 ETCO₂ monitor will be used as the primary device to measure ETCO₂, with a nasal cannula capable of delivering supplemental oxygen and measuring ETCO₂ (Oridion Medical, Needham, MA).

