To assess these outcomes, we will download electronic data from each sedation into a Microsoft Excel database, checked and adjudicated any discrepancies with research associate notations, and generate a graph of the subject's sedation with the X-axis showing time and the Y-axis depicting ETCO₂, SpO₂, respiratory rate, and heart rate. Electronic time stamps noted propofol administration, procedure initiation and completion, adverse events, and physician interventions.

Before study blinding is broken, three investigators will evaluate each graph to code the presence or absence of cerebral hypoxia, peripheral hypoxia and respiratory depression. We will disqualify graphs if they had >35% data loss, unless all three evaluators agreed that there was unequivocal evidence of hypoxia (cerebral and or peripheral) and/or respiratory depression.

6. Withdrawal of Subjects

Participation is voluntary. Subjects may withdraw from this study at any time. If this is the case their data will be deleted. We will record the number of patients that withdraw. Subjects may be withdrawn without their consent if the electronic data cannot be recorded.

Statistical Plan

1. Sample Size Determination

As this is a pilot, prospective, observational trial, no power calculation will be used to measure a difference. In previous propofol studies, approximately 10-30% of patients develop hypoxia, and approximately 50% of patients meet criteria for respiratory depression. Thus, we believe enrolling 100 patients in this observational trial will allow for approximation of any correlations that are measured.

2. Statistical Methods

All clinical observations and demographic data will be summarized using medians with range or means with standard deviations as appropriate. Rate of detection of respiratory depression and hypoxia and timing of these events for each instrument (near-infrared spectroscopy, pulse oximetry, capnography) will be summarized descriptively. Associations among SaO₂, and ETCO₂ will be estimated using spearman's rank correlation coefficient, using within-cluster resampling algorithm. This will allow for estimation of the marginal correlation in the presence of clustered data. Correlations not involving repeated measures data will be estimated with Spearman's rank correlation coefficient. All analysis will be conducted using SPSS software (IBM, Armonk, NY).

Risks to Subjects

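### Single-arm event rates rest on a convenience sample with an open discretion exclusion, and the plan has no step to assess selection into it

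*Combined protocol and SAP*

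**What the plan says.** All references are to the combined protocol and SAP.

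- **Specific Aims.** The main aim is absolute rates: "To measure the rates of hypoxia and respiratory depression requiring a physician intervention in adult patients". There is one group and no comparator.
- **Study Design, opening sentence.** The study is prospective and non-randomised, "using a convenience sample of 100 subjects undergoing sedation for ED procedures".
- **Study Design, 1. Recruitment Methods.** Screening is shared: "The research associates as well as the health care team (both residents and attending physicians) will screen patients". Consent and enrolment belong to the research associates, who screen through the electronic record system. On the sedation itself: "The health care team will be in charge of the procedural sedation and all other management".
- **Study Design, 2. Inclusion and Exclusion Criteria.** After the listed medical exclusions, the list closes with "pregnant women, subjects under police custody, or physician discretion". No criteria are given for the discretion, and no reason has to be recorded.
- **Study Design, 6. Withdrawal of Subjects.** "We will record the number of patients that withdraw". The text specifies no other participant-flow count. It does not ask for the number eligible, missed, refusing or excluded by discretion, or for a comparison of enrolled with non-enrolled patients.

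**The concern.** In a single-arm study the event rate depends directly on who enters, because there is no control group selected in the same way. Here the clinicians who will run the sedation can influence entry, and they can see features that bear on outcome.

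The protocol supplies the link itself. Its Significance section argues that anxious patients may be harder to sedate and may need more propofol, and that more propofol goes with more adverse respiratory events. Anxiety and expected difficulty are visible before enrolment. A clinician might keep such patients out as a precaution, which would lower the observed rates. A clinician might equally steer them in, because nitrous oxide is expected to help them, which would raise the rates.

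The rates will also be read against outside figures. The sample size section cites 10-30% hypoxia and about 50% respiratory depression in earlier propofol work, and the Significance section expects fewer respiratory events than with propofol alone. A rate below those figures could reflect the adjunct, the selection or both. The planned data, as described, would not help a reader tell these apart.

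**Working it through.** **The plan's own figure.** The 100 subjects come from no formula; the sample size section says that no power calculation is used. There is nothing to reproduce, so the check asks how large a selection effect could be and whether the plan would show it.

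**1. Sampling error at n = 100.** At a rate of 30% (top of the plan's hypoxia range), the 95% Wald half-width is 1.96 × √(0.30 × 0.70 / 100) = 0.090, or 9.0 points. The exact 95% interval for 30 events in 100 is 21.2% to 40.0%.

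**2. Hypothetical selection on expected difficulty.** The inputs are assumptions and appear nowhere in the documents: half of eligible patients at 20% risk and half at 40%, so the true rate is 30%. If the low-risk half is *r* times as likely to be enrolled, the expected observed rate is (0.20*r* + 0.40) / (*r* + 1).

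| *r* | Calculation | Observed rate | Bias |
|---|---|---|---|
| 2 | 0.80 / 3 | 26.7% | -3.3 points |
| 3 | 1.00 / 4 | 25.0% | -5.0 points |
| 4 | 1.20 / 5 | 24.0% | -6.0 points |
| 1/2 | 0.50 / 1.5 | 33.3% | +3.3 points |
| 1/4 | 0.45 / 1.25 | 36.0% | +6.0 points |

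The last two rows apply the same assumptions in the other direction.

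**3. Sensitivity to the assumptions.** Alternatively, let a share *s* of eligible patients be passed over, with *RR* times the risk of those enrolled. The observed rate is then *p* / [(1 - *s*) + *s* × *RR*]. Both *s* and *RR* are assumed.

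| True rate *p* | *s* = 10%, *RR* = 1.5 | *s* = 30%, *RR* = 2 |
|---|---|---|
| 30% | 0.30 / 1.05 = 28.6% (-1.4) | 0.30 / 1.30 = 23.1% (-6.9) |
| 50% | 0.50 / 1.05 = 47.6% (-2.4) | 0.50 / 1.30 = 38.5% (-11.5) |

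The result runs from trivial to larger than the sampling error (9.8 points at 50%), depending wholly on inputs the documents do not give.

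**4. Would an interval reveal it?** No. An interval is centred on the observed rate and reflects chance only. Under step 2 with *r* = 2 to 4, an exact 95% interval at n = 100 would contain the true 30% in 92% to 79% of studies, and a Wilson interval in 88% to 72%. A larger sample would narrow the interval around the biased value.

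**5. Would anything else in the plan reveal it?** The one flow count, withdrawals, concerns people already enrolled. It says nothing about those who never entered.

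**The case against.** The strongest case on the other side has several parts.

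- **This is a declared descriptive pilot.** Convenience sampling is stated openly and is common at this stage, and a discretion exclusion is a normal safety provision. That stands. The gap is the missing accounting, not the existence of either feature.
- **The treating team is not the only gatekeeper.** Research associates also screen, and they approach, consent and enrol. That stands too. It reduces the team's influence without removing the discretion clause.
- **Eligibility already narrows the risk spread.** Only ASA 1 or 2 patients enter, and instability, major trauma, shock and sepsis are excluded. This may leave less room for selection than step 2 assumes, and the assumed -3 to -6 points are smaller than the sampling half-width. Both points stand and limit the weight of the concern.
- **The net direction is open.** Graphs with more than 35% data loss are dropped unless all three evaluators agree that an event is unequivocal. That rule tends to keep poor recordings with events and could push rates upward.

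Two stronger readings are tempting and are not supported.

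*That the department's volume shows heavy selection.* The Resources section says that the department "sees approximately 300 patients a day, of which 5% are emergencies that require procedural sedation and analgesia". That is 300 × 0.05 = 15 a day, so 100 subjects equal 100 / 15 = 6.7 days of candidates. Six earlier trials of 100-200 subjects over 7 years would be 600 to 1,200 of 15 × 365 × 7 = 38,325, or 1.6% to 3.1%. Neither figure is evidence of selection. A perfectly consecutive series of 100 would also equal 6.7 days of that pool. The percentages concern other trials whose eligibility rules are not given. The 15 a day is also counted before this trial's exclusions.

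*That selection could never be detected.* Screening runs through the electronic record system, so a retrospective comparison looks feasible although none is planned. The data collection form (Attachment B) is listed but not reproduced, so a screening field on it cannot be ruled out.

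**Conclusion.** The concern holds as a gap in recruitment and reporting. Single-arm rates are to be estimated from a convenience sample with an unrecorded discretion exclusion, the sedating team takes part in screening, and the text plans no step to assess selection. The documents show that bias is possible. They do not show that it will occur, in which direction, or how large it would be.

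The range of about -3 to -6 points is an illustration that rests on the assumed 20%/40% split and the 2- to 4-fold enrolment preference. It should not be quoted as an estimate for this trial. No figure stated in the plan is wrong because of this point. The pilot can run without the change, but its main safety rates would be harder to interpret. The change is worth making because it is cheap and because reasons for discretion are hard to reconstruct afterwards.

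**What to change.** 1. **Study Design, opening sentence.** Replace the convenience sample with *consecutive eligible patients during research associate shifts*, and state the shift hours.
2. **Exclusion criteria.** Keep physician discretion as it is. Require a short reason, entered before nitrous oxide starts (for a patient kept out, before the sedation begins), so that the course of the sedation cannot shape it.
3. **Recruitment Methods.** Have the existing associates keep a minimal de-identified log. Limit it to patients who meet the listed criteria during a shift but are not enrolled: age, sex, ASA class, procedure, and reason (missed, refused, discretion).
4. **Data Management.** Collect the same items for enrolled subjects. Age and gender are listed there; ASA class and procedure type are not, so add them unless Attachment B already has them.
5. **Statistical Methods.** Report participant flow from eligible to analysed, including withdrawals and disqualified graphs, and compare enrolled with eligible-not-enrolled patients descriptively.
6. **Privacy and confidentiality sections.** Extend them to the log, since it holds data on people who have not consented.

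**Cost.** Some clerical time for staff who already screen 7 days a week, possibly slightly slower enrolment, and the privacy wording. Limiting the log to eligible patients avoids recording everyone screened.

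**What remains.** Off-shift patients stay outside the sample, and this should be stated as a limitation. Similarity on four recorded items would not rule out selection on something unrecorded, such as anxiety.
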